Background: This is a single center, Phase I/II, open label single-arm exploratory study. The trial will primarily examine the safety and tolerability of clazakizumab given after the diagnosis of cABMR in 10 subjects (15-75yrs) who exhibit DSAs to their donor. Patients entered will also have been diagnosed with cABMR + TG post-transplant based on Banff 2015 criteria. Patients are required to have a eGFR \geq 30 mL/min/1.73m² as calculated by the MDRD equation (Schwartz equation will be used to estimate CrCl for patients under 18 years of age) at entry. All patients will be recruited from the renal transplant program at Cedars-Sinai Medical Center. Once cABMR is diagnosed, donor-specific anti-HLA antibodies will be assessed (DSA) which are associated with cABMR and/or graft loss. DSA will be detected using solid phase assay systems currently utilized at the Cedars-Sinai Medical Center HLA Laboratory ([name] Director, [contact]. These anti-HLA antibodies may result naturally or from previous pregnancy, transfusions, or prior transplants. Patients treated with clazakizumab for cABMR will have labs for DSAs, and other monitoring labs as well as immunologic studies as outlined (See Study Protocol in Appendix A). In addition to the standard post-transplant immunosuppressive protocol, patients with cABMR will receive clazakizumab 25mg SC given every 4 weeks (30 days) for a total of 6 doses. If no safety/tolerability/efficacy issues are observed after the initial dose, patients will continue the protocol as outlined (see Appendix A). A protocol biopsy will be performed after the 6th and after the 12th doses of clazakizumab (as mentioned before) to assess the allograft for evidence of cABMR/ABMR, including C4d staining and TG using Banff 2015 criteria¹⁴. Banff scoring will be compared between the index and protocol biopsy after cessation of therapy. Patients who have evidence of persistent allograft dysfunction may have non-protocol biopsies for cause. After completion of the clazakizumab therapy, patients will be followed up to assess allograft function and ABMR episodes as well as DSAs. The protocol is summarized in figure 14 below. Monitoring of Treg, Thir, Tfh and plasmablast as well as IL-6

and CRP level will be performed in the Transplant Immunology Lab at Cedars-Sinai Medical Center at select time points ([name] Director, [contact]).

[figure not shown]

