A long term dosing option at conclusion of 12 months (after Study Day 365 visit) For those patients who complete the 12 month protocol, patients may continue to receive clazakizumab 12.5 mg or 25 mg subQ, dosed every 4-8 weeks long term, per PI discretion. Please see Appendix E for long term visit schedule. Biopsies during the long term extension will Page 21

be conducted at 12 months per PI discretion or for cause (suspected rejection). The long term extension of this study is planned as an ongoing protocol, with patients to continue in the LTE if approved on an annual basis by PI and CSL Behring. Participants in the LTE component of the study will be removed if it is determined that there is no longer a clinical benefit of therapy or if there is an observed issue with safety. The LTE will be allowed until clazakizumab is FDA approved in the US or if the study is terminated. The objectives for the LTE are included in Sections 3 and 3.1. Physical exams during the LTE will occur in person or via Video Visit, as per SOC protocol.

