4.6 Infection Prophylaxis Protocols and Viral Monitoring Post-Transplant

All study patients, regardless of their cytomegalovirus (CMV) status, receive IV ganciclovir while inpatients and valganciclovir as outpatients for 6 months post kidney transplant, with dose adjustments for renal function. Fungal prophylaxis was accomplished with fluconazole 100 mg daily for 1 month post transplant. Pneumocystis jirovecii pneumonia and bacterial prophylaxis is accomplished with trimethoprim 80 mg and sulfamethoxazole 400 mg daily for 12 months post transplant. No additional prophylaxis will be needed for patients who are enrolled in this trial more than one year from transplant.

Viral polymerase chain reaction assays for CMV, Epstein Barr virus, Parvovirus B-19, Polyoma virus BK and JC will be performed on study patients monthly for 6 months post-transplantation. Methodologies used for monitoring viral replication have been described previously ²⁵.

5 Dosing of Clazakizumab

For antibody mediated rejection: Clazakizumab will be administered at a dose of 25mg/SC every 4 weeks post pulse methylprednisolone, plasmapheresis, and high dose IVIG. If the patient proceeds to the LTE, they will receive clazakizumab 12.5 mg or 25 mg SC Q4W or Q8W.

Product Description, Storage and Administration Instructions

Clazakizumab will be provided by CSL Behring LLC.

Generic name: Clazakizumab

Active ingredient: Genetically engineered humanized anti-IL-6 mAb

Strength: 12.5 mg/mL (once the 25 mg/mL concentration was no longer available)

Excipients: L-histidine, L-histidine monohydrochloride, sorbitol, polysorbate-80, and water for injection

Appearance: Clear to slightly opaque, colorless to dark yellow-colored solution

Dosage form: Single-dose vials (25 mg/mL or 12.5 mg/mL) for injection.

Manufacturer: Ajinomoto Althea, San Diego CA

Patheon Manufacturing Services LLC, Greenville, NC

Clazakizumab vials should be stored at ≤-20°C (-4°F) with protection from light.

The drug product will be administered undiluted at a concentration of 12.5 mg/mL.

Prepared syringes may be stored for up to 24 hours in a refrigerator, 2°-8°C (36°-46°F), and up to 4 hours of the 24 hours may be at room temperature, 15°-25°C (59°-77°F). The prepared syringes should be protected from light.

Prior to administration, clazakizumab should reach room temperature by storing unrefrigerated for 30 to 60 minutes before use.

IP requests should be sent to: [contact]

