The impact of treatment with clazakizumab on demyelinating disorders is not known; events were rarely reported. Patients should be closely monitored for signs and symptoms potentially indicative of central demyelinating disorders. Physicians should exercise caution in considering the use of clazkizumab in patients with pre-existing or recent onset demyelinating disorders. Treatment with clazakizumab should be interrupted during assessment of a potential demyelination event and only resumed if the benefit of continuing study drug is favorable.

Hematologic Abnormalities and Bleeding Events

Decreases in neutrophil and platelet counts have been observed following treatment with clazakizumab in combination with MTX. In addition, there may be an increased risk of neutropenia in patients who have previously been treated with a TNF antagonist.

For patients with concomitant medications associated with hematologic toxicity, the reduction or interruption of the suspected medication is recommended prior to modifying clazakizumab.

Table 2: Neutropenia Risk Mitigation

ANC (cells/mm³)	Action
> 1000	Maintain dose.
500 – 1000	Interrupt clazakizumab dosing.
	When ANC increases to > 1000, resume clazakizumab 25mg SQ monthly
< 500	Discontinue clazakizumab.

Table 3: Thrombocytopenia Risk Mitigation

Platelet count (cells/mm³)	Action
> 100,000	Maintain dose.
50,000 - 100,000	Interrupt clazakizumab dosing.
	When platelet count increases to > 100,000, resume
	Clazakizumab at 25mg SQ monthly
< 50,000	Discontinue clazakizumab.

Elevated Liver Enzymes and Hepatic Events

Elevations in ALT and AST have been observed during treatment with the study medications

Table 4:

Lab Value	Action
> 1 to 3x ULN	Dose modify concomitant transplant immunosuppressive drugs if appropriate For persistent increases in this range, interrupt clazakizumab until ALT/AST have normalized

	Restart with 25mg SQ monthly as clinically appropriate				
> 3 to 5x ULN	Interrupt clazakizumab dosing until < 3x ULN and follow				
(confirmed by repeat	recommendations above for >1 to 3x ULN				
testing)	For persistent increases > 3x ULN, discontinue Clazakizumab				
	Discontinue clazakizumab if total bilirubin >2 x ULN				
> 5x ULN	Discontinue clazakizumab				

Cardiovascular Events and Elevated Lipids

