Appendix C: DSMB Charter & FDA Guidance for Clinical Trial Sponsors

Appendix D: Safety Reporting Forms

Appendix E Study/Protocol: A Phase I/II Trial to Evaluate the Safety and Tolerability of Clazakizumab® (Anti-IL-6 monoclonal) As an Agent to Eliminate Donor Specific HLA Antibodies (DSAs) and Improve Outcomes of Patients with Chronic & Active Antibody-Mediated Rejection (cABMR) Post-Kidney Transplantation

The below schedule to repeat annually (Visit 1 – 6) per PI discretion

Study visit	Visit 1 Follow up	Visit 2 Week 8 -	Visit 3 Week 16	Visit 4 Week 24 -	Visit 5 Week 32-	Visit 6 Week 40-
		7d/+	-7d/+	7d/+	7d/+	7d/+
	year Day 0	10days	1 '	10days		
	CLAZ#1 %	Todays	10days	Todays	10days	10days
NA - P - 11P - 1	CLAZ#1 %	-	+		-	
Medical History			-			
Complete Physical Exam						
Vital signs/weight	X	X	X	X	X	X
Safety laboratory tests	х	Х	x	х	х	X
(CBC with differential, CMP, UA) [^]	^	^				
EBV, CMV, PBK DNA PCR^				X		
IgG^				Х		
CRP^				Х		
Donor – specific antibodies (DSA)^						
CNI Levels^	X	X	X	X	X	X
TB testing [Quantiferon TB Gold]						
Clazakizumab injection	X #1%	X #2	X #3	X #4	X #5	X #6
Estimated GFR (using MDRD equation or Schwartz						
equation will be used to estimate CrCl for patients	X	X	X	X	X	X
under 18 years of age)						
Pregnancy test (for WOCP) ²	X	X	X	X	X	X
Concomitant Med Review	Х	Х	X	Х	Х	Х
Kidney Biopsy						
Review of allograft loss						
Review of non-protocol biopsy results						
Adverse Event Monitoring	X	Х	X	Х	Х	Х

Day 365 ± 30 days #
X#
X#
X#
X#
X#
X#
X&#	

	

	

	

	

	

V##	

X*#	

X# X#	

A#	

	

& TB testing to be

completed once a year. TB test will be collected if not done in the last 2 months.

- ^ At or within 1 month prior to appointment
- 1. DSA to be collected prior to clazakizumab infusion.
- 2. Women of child bearing age is between 12-55 years old.
- * At 12 Months Per PI discretion (any other biopsies will be conducted for cause)
- % Timed minimum 4 weeks from last clazakizumab dose
- # Visit should be combined with either visit 1, 2, 3, 5, or 6. Depending on which visit is closest to day 365

Study visit	Visit 1	Visit 2	Visit 3	Visit 4	Visit 5	Visit 6
	Follow up	Week 4	Week 8	Week 12	Week 16	Week 20
	year	-2d/+	-2d/+	-2d/+	-2d/+	-2d/+
	CLAZ#1 %	10days	10days	10days	10days	10days
Medical History						
Complete Physical Exam						

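### Tables 2 and 3 restart every patient at 25 mg monthly, so an extension patient on a reduced regimen would resume after a cytopenia at about 2 and at most about 4 times the previous dose intensity

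*Protocol*

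**What the plan says.** The 12-month phase has a single regimen. Section 4 states that "patients with cABMR will receive clazakizumab 25mg SC given every 4 weeks (30 days) for a total of 6 doses", and patients who go on after month 6 continue monthly.

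The extension has several. Section 4 says "patients may continue to receive clazakizumab 12.5 mg or 25 mg subQ, dosed every 4-8 weeks long term, per PI discretion". Section 5 is more specific: "If the patient proceeds to the LTE, they will receive clazakizumab 12.5 mg or 25 mg SC Q4W or Q8W".

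The toxicity rules are in Section 5.3:

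- **Table 2**, ANC 500 to 1000: interrupt, then "When ANC increases to > 1000, resume clazakizumab 25mg SQ monthly".
- **Table 3**, platelets 50,000 to 100,000: interrupt, then on recovery above 100,000 resume "Clazakizumab at 25mg SQ monthly".
- **Table 4**, ALT/AST up to 3 times ULN and persistent: interrupt until normal, then "Restart with 25mg SQ monthly as clinically appropriate". Elevations of 3 to 5 times ULN that fall back are referred to the same row.

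Table 4 leaves room for judgement. Tables 2 and 3 do not.

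Appendix E schedules the safety panel ("CBC with differential, CMP, UA") at the dosing visits of both extension schedules, the eight-weekly and the four-weekly one.

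**The concern.** The restart dose in the tables is the regimen of the 12-month phase, written as a fixed number and not as the patient's own regimen. In that phase the two coincide. In the extension they need not: for a patient on 12.5 mg, or on an interval longer than four weeks, the tables prescribe a higher dose, a shorter interval, or both. This happens at the moment when the patient has just recovered from a drop in neutrophils or platelets, both of which Section 2 lists as identified risks of clazakizumab.

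Two things are at stake. The first is patient safety: a table meant to mitigate risk would increase drug exposure after a toxicity. The second is interpretation: the first long-term objective in Section 3 is safety and efficacy at 12.5 mg or 25 mg every 4 to 8 weeks, and an unintended change of regimen triggered by toxicity blurs what was observed at which dose.

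**Working it through.** **Do the tables reach the extension?** Four parts of the protocol bear on this.

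1. Section 5 sets the extension doses, and Section 5.3 with its tables belongs to the same chapter. No sentence restricts the tables to the first 12 months.
2. Section 5.2 has subjects evaluated, at each visit throughout their participation, for events that require interruption or discontinuation. This concerns monitoring and does not settle the restart dose, but it shows that toxicity management is not meant to end at day 365.
3. Appendix E schedules the blood count at extension dosing visits, so these cytopenias would be detected there.
4. Neither the extension text in Section 4 nor Appendix E gives another restart dose.

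**Size.** The protocol states no figure to reproduce. Nominal dose intensity is dose divided by interval, and the ratio is restart intensity divided by previous intensity. Monthly can be read as 28 days (four weeks) or as 30 days (the protocol's own gloss in Section 4). The restart intensity is then 25/28 = 0.893 mg/day or 25/30 = 0.833 mg/day.

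| Previous extension regimen | Previous intensity (mg/day) | Ratio, 28-day month | Ratio, 30-day month |
|---|---|---|---|
| 25 mg Q4W | 25/28 = 0.893 | 1.00 | 0.93 |
| 25 mg Q8W | 25/56 = 0.446 | 2.00 | 1.87 |
| 12.5 mg Q4W | 12.5/28 = 0.446 | 2.00 | 1.87 |
| 12.5 mg Q8W | 12.5/56 = 0.223 | 4.00 | 3.73 |

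The 30-day column sets a 30-day restart interval against exact 28- and 56-day extension intervals. If the extension intervals are also read as 30 and 60 days, the ratios return to 1, 2, 2 and 4.

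Section 4 also permits intervals between four and eight weeks. With a 28-day month, the ratio for 25 mg is 1.25 at five weeks (35/28) and 1.75 at seven weeks (49/28). For 12.5 mg it is twice that, 2.5 to 3.5. Every reduced regimen is therefore escalated, and 4.0 remains the maximum.

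**With the change proposed below**, the ratio is at most 1.0 for every regimen.

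**The case against.** The strongest reply is that the protocol contains a conflict, not an order to escalate. The extension provisions are the more specific ones, Section 4 puts dose and interval at the principal investigator's discretion, and resuming can be read as returning to the assigned regimen. The row for normal counts, which leaves the dose unchanged, fits that reading. An investigator who restarted at 12.5 mg Q8W would comply with Sections 4 and 5. This lowers the chance of an automatic escalation. It does not remove the problem: the tables are the specific instruction for restarting after toxicity, nothing says that the discretion overrides them, and two texts that disagree on a dose after toxicity need to be reconciled.

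The other safeguards help less. An extension patient can be removed "if there is an observed issue with safety", but that clause gives no restart dose, and the tables expressly provide for resumption at these counts. DSMB re-evaluation under Section 6 is triggered by SAEs, severe infusion-related or infectious complications, or worsening ABMR, and an isolated ANC of 500 to 1000 need not be any of these. The advice to reduce or interrupt a suspected concomitant drug first makes an interruption of clazakizumab less likely, but does not change the dose once it is restarted.

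Three limits stand:

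- 25 mg every four weeks is a permitted extension regimen and the one assigned in the first 12 months, so the escalation never exceeds the protocol's ceiling.
- The ratios are nominal. With a mean half-life of 31.1 to 33.6 days after SC dosing in healthy men (Section 2), the higher exposure would build up over repeated doses and not appear with the first.
- Few patients can be affected.

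**Conclusion.** The concern holds. Tables 2 and 3 fix a restart dose that suits the 12-month phase and, taken literally, escalates extension patients on a reduced regimen: 2.0 times for 12.5 mg Q4W or 25 mg Q8W, 4.0 times for 12.5 mg Q8W, and 1.25 to 3.5 times for the five- to seven-week intervals, all with a 28-day month. Patients in the first 12 months and extension patients on 25 mg Q4W are not affected.

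This rests on reading the tables as applying throughout the study, which no text contradicts, and on the investigator following them instead of using the general discretion over extension dosing. How many of the 10 patients reach a reduced regimen is not stated. The point does not touch eligibility or the safety analysis of the 12-month phase. It should be corrected because it concerns dosing after toxicity and is easily put right.

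**What to change.** Keep 25 mg monthly in Tables 2 to 4 for the 12-month phase. Add one line to each table for the extension: resume at a dose no higher, and an interval no shorter, than in use before the interruption. Table 4 already allows clinical judgement, so the change there is for consistency; a single sentence ahead of the tables that covers all three would serve equally well. Recording the regimen in use at each adverse event would help the long-term safety assessment but is optional. The cost is a wording amendment, with no new data and no new visits.

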Two studies were terminated prematurely due to safety concerns. A Phase 2 study in Crohn's was terminated early because of GI perforation in 3 subjects who had received clazakizumab and this indication is no longer being studied. Although these subjects had multiple confounding medical issues, and the disease itself has an inherent risk of mucosal perforation, gastrointestinal perforations were also observed during the clinical studies with tocilizumab in patients with RA. Gastrointestinal perforation is a recognized risk of anti-IL-6 mAbs. After only 3 subjects were enrolled, a study in subjects with GVHD was also prematurely terminated due to 2 subjects experiencing similar serious adverse events (SAEs) (i.e., acute renal failure) which led to death. Both subjects had severe GVHD disease at the time of death.

Overall, the safety findings from the clinical studies conducted with clazakizumab to date are consistent with the known effects of blocking the IL-6 pathway (see Actemra® prescribing information]). Identified risks associated with clazakizumab administration include the following: infections, liver function test (LFT) abnormalities, changes in hematology parameters (i.e., neutropenia and thrombocytopenia), dyslipidemia (i.e., hypercholesterolemia and hypertriglyceridemia), and gastrointestinal perforations.

For further details regarding clinical studies with clazakizumab, please consult the Investigator's Brochure.

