3.0 Primary Objectives

This study will be an open label design to assess the safety and efficacy of clazakizumab 25 mg SC given every 4 weeks (30 days) for a total of 6 doses in eliminating DSAs and stabilizing clinical features of cABMR in patients who have biopsy proven severe cABMR +TG. If improvements are seen in pathologic features of antibody mediated rejection from this biopsy compared to index biopsy, we will offer patients the opportunity to continue clazakizumab administrations monthly for an additional 6 months. A one year biopsy will then be performed at the end of the study. Safety determinations will be aimed at assessments of any side effects associated with clazakizumab administration and risk for infectious complications associated with clazakizumab therapy. Limited efficacy determinations will include assessment

of composite surrogate end points including patient and graft survival, stabilization of the clinical features of cABMR (eGFR, SCr) after clazakizumab treatment, and safety throughout study duration.

Long term primary objectives include:

- 1. assess the safety and efficacy of clazakizumab 12.5 mg or 25 mg SC given every 4-8 weeks in eliminating DSAs and stabilizing clinical features of cABMR in patients who have biopsy proven severe cABMR +TG
- 2. assess composite surrogate end points including patient and graft survival, stabilization of the clinical features of cABMR (eGFR, SCr) after clazakizumab treatment, and safety throughout study duration

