Patients with RA have an increased risk for cardiovascular disorders, therefore, risk factors for cardiovascular disease (eg, hypertension, hyperlipidemia) should be managed as part of their standard of care. See section on Drug Interactions.

For patients with LDL cholesterol ≥160 mg/dL, it is strongly recommended that investigators advise therapeutic lifestyle changes that may include initiation lipid-lowering agents. Lipid-lowering agents should also be considered for patients with lower LDL cholesterol levels as part of their therapeutic lifestyle changes depending on their overall risk as defined in NCEP ATP III or other national guidelines.

Malignancies

The impact of immunosuppression on the development of malignancies is not known, however an increased rate of some malignancies, notably lymphoma, has been observed in RA patients. Although no imbalance of malignancies was observed in clinical trials of clazakizumab, malignancies have been identified as a concern for other biologics. It is recognized that identification of such events in clazakizumab-treated patients may require a longer period of surveillance. Clazakizumab should be discontinued in patients with malignancies (with the exception of local basal or squamous cell carcinoma of the skin that is completely excised with free margins).

Hypersensitivity or Anaphylaxis:

An infusion/dose reaction is defined as an adverse event occurring during and within 24 hours after the infusion or subcutaneous injection of clazakizumab. This may include hypersensitivity reactions or anaphylactic reactions.

Signs of a possible hypersensitivity reaction include but are not limited to:

- · fever, chills, pruritus, urticaria, angioedema, and skin rash.
- cardiopulmonary reactions, including chest pain, dyspnea, hypotension or hypertension.

Healthcare professionals administering clazakizumab should be trained in the appropriate administrative procedures, be able to recognize the symptoms associated with potential anaphylactic or hypersensitivity reactions, and have the appropriate medication available for immediate use in case of anaphylaxis or hypersensitivity reaction during or after

administration of clazakizumab. Healthcare professionals should also instruct patients to seek medical attention if they experience symptoms of a hypersensitivity reaction outside of the clinic.

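### Neither long-term extension schedule in Appendix E includes a lipid test, although dyslipidemia is an identified risk and Section 5.3 ties advice to an LDL value

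*Protocol*

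**What the plan says.** Section 2.0 (Clinical Efficacy and Safety Studies) lists five identified risks of clazakizumab: infections, liver test abnormalities, hematology changes, "dyslipidemia (i.e., hypercholesterolemia and hypertriglyceridemia") and gastrointestinal perforation.

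Section 5.3 (Cardiovascular Events and Elevated Lipids) opens with patients who have rheumatoid arthritis and says that cardiovascular risk factors, hyperlipidemia among them, "should be managed as part of their standard of care". The next paragraph is not limited to that population: "For patients with LDL cholesterol ≥160 mg/dL, it is strongly recommended that investigators advise therapeutic lifestyle changes", and these may include a lipid-lowering agent. Such agents are also to be considered at lower LDL, "depending on their overall risk as defined in NCEP ATP III or other national guidelines".

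The first long-term primary objective in Section 3.0 is to "assess the safety and efficacy of clazakizumab 12.5 mg or 25 mg SC given every 4-8 weeks". Section 4 leaves the extension open-ended: "The LTE will be allowed until clazakizumab is FDA approved in the US or if the study is terminated". Appendix E gives one eight-weekly and one four-weekly schedule, under the instruction "The below schedule to repeat annually". In both tables the safety laboratory tests are "CBC with differential, CMP, UA".

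**The concern.** Section 5.3 can be followed only if the patient's LDL is known. Appendix E, which fixes what is measured in the extension, never asks for it, and it does not say that routine-care values will be used instead.

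Raised lipids usually cause no symptoms. The adverse event and medication reviews at each visit will therefore find them only if someone has ordered a test outside the protocol. A patient whose LDL rises past 160 mg/dL during the extension may not receive the advice that the protocol strongly recommends. Dosing is monthly or two-monthly with no planned end, so this exposure can last for years.

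The Drug Interaction text of Section 5.3 adds a lesser reason. It names atorvastatin among the drugs whose effect should be watched when clazakizumab is started or stopped. For a statin, that effect is read from lipid values.

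**Working it through.** The plan states no figure to reproduce. The check is a count of what Appendix E schedules, set against the risks and advice elsewhere in the protocol.

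**1. Rows in each Appendix E table.** Medical history, physical exam, vital signs, safety laboratory tests, viral PCR, IgG, CRP, DSA, CNI levels, TB test, injection, eGFR, pregnancy test, concomitant medication, biopsy, allograft loss, non-protocol biopsy and adverse events: 18 rows. Nine are laboratory rows (safety tests, PCR, IgG, CRP, DSA, CNI, TB, eGFR, pregnancy). Rows naming lipids: 0.

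**2. Footnotes in each table.** They cover TB testing, the one-month window for laboratory tests, DSA timing, child-bearing age, biopsy, dose timing and the combined Day 365 visit: 7 footnotes. Footnotes naming lipids or the collection of routine lipid results: 0.

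**3. Identified risks against scheduled tests.** Of the five risks in Section 2.0, three are defined by laboratory values (this grouping is mine, not the protocol's).

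| Identified risk | Test in Appendix E | Numbered visits with the test |
|---|---|---|
| Liver test abnormalities | CMP | 6 of 6 |
| Hematology changes | CBC with differential | 6 of 6 |
| Dyslipidemia | none | 0 of 6 |

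This takes CBC and CMP in their ordinary meaning. A CMP does not include lipids.

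**4. Could the broken Day 365 column hide a lipid test?** No. A mark in that column needs a row to belong to, and there is no lipid row.

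**5. Does the standard-of-care wording fill the gap?** It says how hyperlipidemia is to be managed. It sets no test, no interval and no recording. Where the protocol relies on routine care for an assessment, it says so: Appendix A marks the ECG and chest X-ray as SOC, and Section 4 does the same for physical exams in the extension.

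**6. Where a panel would fit.** PCR, IgG and CRP are already drawn once mid-schedule: at Visit 4 (week 24) in the eight-weekly table and Visit 6 (week 20) in the four-weekly table. The Day 365 footnotes combine that visit with Visit 1, 2, 3, 5 or 6 (eight-weekly) or Visit 1, 2, 3, 4 or 5 (four-weekly), so it does not coincide with the mid-year draw.

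**7. Number of assays.**
- Two panels per patient per year: 2 × 10 subjects = 20 a year at most, if all 10 enter the extension.
- The four-weekly table spans 6 × 4 = 24 weeks and does not say whether it is run twice in a year. If it is (an assumption), Visit 6 falls at weeks 20 and 44. With Day 365 that makes 3 panels per patient, and 3 × 10 = 30 a year at most.

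**The case against.** The strongest reply is that the protocol breaks no promise. The LDL advice is conditional, no objective names a lipid outcome, and hyperlipidemia is assigned to standard of care, which can hardly be delivered without measuring lipids. Liver and blood-count values drive interruption and discontinuation rules in Tables 2 to 4, so they must be scheduled. Lipids drive no dosing decision, and leaving them to routine care at a transplant center is a coherent choice. The lipid text also reads partly like general guidance for rheumatoid arthritis.

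Much of this stands. The LDL advice is not a dosing rule, a routine result could prompt it, and nothing in the protocol shows how often lipids would go unchecked. A reported abnormality or a new statin would be picked up at the visit reviews.

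The gap nevertheless remains. The protocol attributes dyslipidemia to clazakizumab itself, and the LDL paragraph is not restricted to rheumatoid arthritis. Managing a risk factor as standard of care fixes neither when it is measured nor whether the study learns the value.

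One limit on the check: the text between the Appendix A table and Appendix C, where the contents list places Appendix B (Send out Labs), was not available. Lipid testing in the first 12 months therefore cannot be ruled out entirely, although no visible Appendix A row shows it. The point is confined to the two Appendix E schedules, whose rows and footnotes can be read.

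**Conclusion.** The point holds. In the extension, dyslipidemia is the only one of the three laboratory-defined identified risks with no scheduled test, and the protocol makes no provision for collecting routine lipid values. The advice in Section 5.3 therefore depends on tests ordered outside the protocol, for an open-ended period in which safety is a primary objective.

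The size is modest. At most 10 patients are concerned, and the number who would miss the advice cannot be estimated from the protocol. No sample size, power or error rate is affected. The gain from testing is individual patient safety: an uncontrolled study of 10 subjects could not estimate a drug effect on lipids. This is an inexpensive improvement, not a flaw that threatens the trial.

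**What to change.** Add a lipid panel row to both Appendix E schedules, using blood already drawn:

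- at the mid-year visit that carries PCR, IgG and CRP (Visit 4, week 24, in the eight-weekly schedule; Visit 6, week 20, in the four-weekly schedule);
- at the Day 365 visit.

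The cost is at most 20 assays a year, or 30 if the four-weekly block runs twice, with no added visit or procedure.

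If the sponsor prefers to rely on routine care, Appendix E should say so and require the values to be recorded with their dates. That is the weaker option, because it still leaves the timing of the test to chance.
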